Figure 2. Enhanced uptake of exercise-induced exosomes by adipose. Exosomes were isolated from serum of mice that had either undergone sham (Control) or synergist ablation (Resistance Exercise, RE) for one day. Isolated exosomes were fluorescently labeled and then reintroduced to the circulation of a naïve mouse by tail vein injection. Tissue was collected after 1 hr, lysed and fluorescence measured. Fluorescence signal was increased 2.3-fold in adipose following injection of labeled exosomes from exercised mouse compared to sham-control mouse.

[figure not shown]

Figure 3. Exosome characterization following hypertrophic growth stimulus. The mouse plantaris muscle was subject to synergist ablation, a model of resistance exercise (RE), to induce a hypertrophic stimulus. **A**, Western blot analysis confirmed exosome isolation from mouse serum using the ExoQuick protocol based on detection of markers of extracellular vesicles Tsg101, CD81 and CD63. **B**, NanoSight analysis of exosomes showed a mean particle size of ~100 nm, indicative of exosomes, with a trend ($p = 0.07$) for decreased particle size following a single day of RE. **C**, Nanosight analysis showed no difference in exosome concentration between groups. Data are presented as mean \pm SEM ($n = 6$ /group).

[figure not shown]

Figure 4. Inhibition of exosome release prevents increase in adipocyte miR-1 expression. Mice were treated with either vehicle (3% DMSO in sterile saline) or the neutral sphingomyelinase inhibitor GW4869 to prevent the release of exosomes. **A**, NanoSight analysis demonstrated that GW4869 treatment reduced serum exosome concentration by >90%. Blocking exosome release by GW4869 treatment prevented the resistance exercise-induced decrease in miR-1 in muscle (**B**); and the increase in miR-1 abundance in exosomes (**C**) and adipose (**D**). Data were normalized to the respective sham control (yellow dotted line) and presented as mean \pm SEM ($n = 4-6$ /group) with significance ($p < 0.05$) denoted by an asterisk.

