showed the isolated extracellular vesicles were within the range (73-139 nm) of exosomes (~30-150 nm) and that exosome serum concentration did not change in response to RE (Fig. 3B-C)⁷⁰.

[figure not shown]
We next determined if the increase in adipose miR-1 abundance after a single day of RE was the result of exosome delivery. This was critical because of an alternative scenario in which miR-1 is released into circulation by damaged muscle (as the result of RE) and travels to adipose tissue bound to lipoproteins or

Ago2⁷¹. Mice were treated with vehicle or GW4869 for seven days prior to either sham or synergist ablation surgery. GW4869 is an inhibitor of neutral sphingomyelinases which has been shown to effectively block the release of exosomes⁷². Nanoparticle tracking analysis confirmed GW4869 treatment effectively reduced serum exosome concentration by over 90% (Fig. 4A). GW4869 treatment prevented the decrease in skeletal muscle miR-1 expression in response to a single day of RE (Fig. 4B) indicating exosome release was

necessary for the down-regulation of skeletal muscle miR-1 expression. Consistent with this finding, GW4869 treatment also prevented the increase in exosomal miR-1 abundance observed with RE and the subsequent increase in miR-1 abundance in adipose tissue (Fig. 4C-D). Together, these findings provide compelling evidence that miR-1 is exported from skeletal muscle by exosomes following RE and exosomal delivery of miR-1 is responsible for the increase in adipose miR-1 abundance.

[figure not shown]

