An overall strength of the proposed experimental design is a shared set of techniques which will facilitate the comparison of results from the mouse (Aim 1), cell culture (Aim 2) and human subjects (Aim 3). The shared set of techniques includes exosome isolation, exosome miRNA loss- and gain-of-function studies, gene expression analysis and catecholamine sensitivity assay. Each of these techniques will be briefly described below and subsequently referred to as the SOP section. Aim-specific methods will be provided in each aim.

Standard Operating Procedures (SOP)

Exosome isolation. Exosomes will be isolated using Exoquick-LP (mouse serum) or ExoQuick-TC (human plasma and culture media) according to the manufacturer's instructions. Briefly, following centrifugation (3000 g, 15 min) exosome precipitation solution will be added to filtered (0.22 um) supernatant, incubated overnight at 4°C with ExoQuick solution and then centrifuged at 1,500 g for 5 minutes to remove all traces of fluid. The exosome pellet will be resuspended into 25ul of PBS. While the exosome field has yet to reach a consensus on the best method for isolating exosomes, ExoQuick has recently been shown to be as good (50-fold > yield), if not better, than traditional ultracentrifugation methods^{77,78}. We will confirm exosome isolation by Western blot, nanoparticle tracking analysis (ZetaView) and transmission electron microscopy⁷⁸.

Exosome miRNA loss- and gain-of-function. Exosomes derived from Control or RE serum (~1 × 10⁶ particles) will be combined with 20 pmol miR-1 mimic or inhibitor and 10 µl Exo-fect solution and then incubated at 37°C for 10 min. Transfected exosomes will be then mixed with 30 µl ExoQuick-TC and incubated at 4°C for 30 min. After centrifugation of samples (14,000 rpm for 3 min), the transfected exosomes will be suspended in PBS.

Gene expression analysis. Total RNA will be isolated from either skeletal muscle or adipose using Direct-zol with 0.5 µg of DNase-treated RNA used to make cDNA using the SuperScript™ VILO™ cDNA Synthesis Kit. Taqman gene expression assays for the following genes: β3-AR, C/EBP2α, HSL, ATGL, TGL, PLIN1, FABP2, FABP4 and AP-2α. miRNAs expression/abundance of muscle, adipose and exosomes will be determined using the miRCury RNA isolation kit and LNA™ Universal RT microRNA PCR system.

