Experiment 1.2. To determine if miR-1 is necessary and sufficient to enhance adipocyte catecholamine sensitivity, Control exosomes will be transfected with miR-1 mimic (Control-plus) and RE exosomes with anti-miR-1 oligonucleotide (RE-minus). These modified exosomes will be incubated with 3T3-L1 adipocytes for 24 hr and then gene expression and catecholamine sensitivity measured as described in the SOP section.

Experiment 1.3. Based on our preliminary data, we hypothesize that RE-induced exosomal miR-1 is repressing expression of AP-2 α , a negative regulator of C/EBP α . To determine if AP-2 α is a target gene of miR-1 we will generate a luciferase reporter gene harboring the 3'-UTR of AP-2 α . We will assess the ability of miR-1 to

repress reporter gene expression; if so, then we will repeat the experiment with a mutant AP-2 α 3'-UTR reporter gene in which the predicted miR-1 binding site is mutated as previously described by us²⁴.

Experiment 1.4. Microarray analysis of epididymal adipose showed increased expression of genes involved in β -adrenergic signaling and lipolysis in response to RE that was blocked by GW4869 treatment (see Fig. 5). The purpose of this experiment is to use qPCR to confirm the microarray results and, importantly, determine if the observed changes in gene expression and effects of GW4869 treatment are the same in female mice (n=12/sex).

Statistical Analysis. A two-factor ANOVA (treatment X sex) will be used to determine if a significant interaction exists between factors for each dependent variable under consideration. If a significant interaction is detected, Scheffé post-hoc comparisons will be performed to identify the source of significance with $p \leq .05$.

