Following a brief rest period, subjects will perform two lower body RE tasks to failure (knee extension and leg press) with blood samples drawn pre- and immediately, 30, 60 and 90 minutes post-exercise. Biopsies of the vastus lateralis and abdominal subcutaneous adipose tissue will be obtained pre- and post-exercise (at approximately 60 and 90 min post, respectively; see graphic abstract in the Human Subjects section).

Experiment 3.1. Exosomal, muscle, and adipose miR-1 abundance will be quantified, as well as miR-1A/B primary transcripts in muscle and adipose by qPCR as described in the SOP section.

Experiment 3.2. Isolated exosomes from the 30 and 60 minute time points will be applied to differentiated ADHASC for 24 hr, and lipolysis *in vitro* and the β AR-3 pathway gene expression assessed as described in the SOP section. Pre-RE exosomes will be transfected with miR-1 mimic (Pre-plus) and 30 minute post-RE exosomes with anti-miR-1 oligonucleotide (Post-minus) and compared to mock transfected exosomes from those time points. These modified exosomes will be incubated with differentiated adipocytes to parallel Aim 1 mouse Experiments 1.1 and 1.2.

Methods.

Resistance exercise (RE). Following determination of each subject's one repetition max (1-RM, see Human Subjects section for detailed description), subjects will perform two exercises, knee extension and leg press at 80% of 1-RM, designed to work the quadriceps. Subjects will perform three sets of eight repetitions, with a 90-120 second rest between sets, with a fourth set performed to failure. RE will be performed on pneumatic resistance devices (Keiser Sports Health Equipment, Fresno, CA).

Muscle biopsy. A muscle biopsy will be obtained from the vastus lateralis at baseline and approximately 1 hr post-exercise under local anesthetic (1% Xylocaine HCl, 3cc). A 1/4 inch wide incision will be made and a sterile 5mm Berkstrom biopsy needle (Pelomi Industries, Denmark) inserted with suction to obtain a 100-200 mg muscle sample. [name], study physician and co-investigator on this project, has extensive experience with this procedure. It is well-tolerated and volunteers routinely provide multiple samples^{83,89,94-96}. Muscle is snap frozen in liquid nitrogen and stored at -80°C until RNA isolation.

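### The mimic and inhibitor arms cannot separate vesicle-delivered miR-1 from carried-over oligonucleotide: the loading step uses a very large excess, removal is not checked, and there is no particle-free control

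*Combined protocol and SAP*

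**What the plan says.** The SOP paragraph on exosome miRNA loss- and gain-of-function gives the only loading recipe in the document: "Exosomes derived from Control or RE serum (~1 × 10⁶ particles) will be combined with 20 pmol miR-1 mimic or inhibitor", with Exo-fect, for 10 minutes at 37°C. It names serum exosomes, but the Approach lists the technique among those shared by all three aims, so I read it as also covering the myotube exosomes of Experiment 2.3 and the human exosomes of Experiment 3.2.

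Clean-up starts with a precipitation: "Transfected exosomes will be then mixed with 30 µl ExoQuick-TC and incubated at 4°C for 30 min". The product is then recovered by a single spin, which the SOP describes as follows: "After centrifugation of samples (14,000 rpm for 3 min), the transfected exosomes will be suspended in PBS". No wash, nuclease step or measurement of the load follows.

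On vesicle size, the Figure 3 legend reports: "NanoSight analysis of exosomes showed a mean particle size of ~100 nm". The Preliminary Data text says that nanoparticle tracking "showed the isolated extracellular vesicles were within the range (73-139 nm", against a defining range for exosomes of about 30 to 150 nm.

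The arms that depend on the recipe are:

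- **Experiment 1.2:** Control-plus and RE-minus. Its stated purpose is "To determine if miR-1 is necessary and sufficient to enhance adipocyte catecholamine sensitivity". No mock-transfected or particle-free comparator is named.
- **Experiment 2.3:** Control-plus and Stim-minus, with the same purpose for muscle-derived exosomes. No such comparator is named here either.
- **Experiment 3.2:** "Pre-RE exosomes will be transfected with miR-1 mimic (Pre-plus) and 30 minute post-RE exosomes with anti-miR-1 oligonucleotide (Post-minus", each compared with mock-transfected exosomes from the same time point.

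**The concern.** These arms are meant to attribute the adipocyte response to miR-1 carried by exosomes. The Aim 1 section on expected outcomes treats a match between Control-plus and RE exosomes as confirming exosomal delivery. That inference needs the mimic or inhibitor to reach the adipocyte with the vesicle.

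If free or Exo-fect-complexed oligonucleotide stays in the pellet, there is a second route. Carried-over mimic could raise miR-1 in the adipocyte with no help from a vesicle. Carried-over inhibitor could neutralise miR-1 inside the adipocyte and not in the exosome. Either would produce the predicted pattern.

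The sponsor recognises the same problem elsewhere. The Preliminary Data consider that miR-1 might reach fat bound to lipoproteins or Ago2, treat ruling this out as essential, and use GW4869 to do so in mice. The loading arms have no comparable safeguard.

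At stake is the mechanistic claim in Experiments 1.2 and 2.3, and its human parallel in Experiment 3.2.

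**Working it through.** The plan states no copies-per-vesicle or capacity figure, so there is none to reproduce.

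**Inputs from the document.** 20 pmol of oligonucleotide; about 1 × 10⁶ particles; mean diameter about 100 nm, observed range 73 to 139 nm, upper end of the defining range 150 nm.

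**Assumptions not in the document.** Volume of one oligonucleotide:

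- single strand, 7 kDa at 0.55 cm³/g: 7,000 × 0.55 / 6.022 × 10²³ × 10²¹ = 6.4 nm³
- duplex, 14 kDa: 12.8 nm³
- 22-base-pair duplex as a cylinder of radius 1 nm: π × 1² × (22 × 0.28) = 19.4 nm³

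**Step 1, amount offered.** 20 × 10⁻¹² × 6.022 × 10²³ = 1.204 × 10¹³ molecules. Divided by 10⁶ particles, this is 1.204 × 10⁷ per vesicle.

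**Step 2, ceiling on capacity.** Sphere volume (4/3)π(d/2)³ divided by the oligonucleotide volume. The outer diameter is used, with nothing subtracted for membrane or water, so this overstates capacity. Ranges below run over 6.4 to 19.4 nm³.

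| Diameter | Volume (nm³) | Most copies that fit | Offered ÷ ceiling | Largest share inside |
|---|---|---|---|---|
| 73 nm | 203,689 | 10,525 to 31,861 | 378 to 1,144 | 0.09 to 0.27% |
| 100 nm | 523,599 | 27,056 to 81,901 | 147 to 445 | 0.2 to 0.7% |
| 139 nm | 1,406,187 | 72,663 to 219,955 | 55 to 166 | 0.6 to 1.8% |
| 150 nm | 1,767,146 | 91,315 to 276,416 | 44 to 132 | 0.8 to 2.3% |

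The most favourable case (150 nm, single strand) still leaves 100 − 2.3 = 97.7% outside.

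**Step 3, what clean-up would have to achieve.** If clean-up removed 99% of the oligonucleotide, 0.01 × 1.204 × 10⁷ ≈ 120,000 free copies per particle would remain, more than the 100 nm ceiling. For free copies merely to equal that ceiling, the fraction left could be at most 81,901 / (1.204 × 10⁷ − 81,901) ≈ 0.7%, or 0.2% with 27,056 copies. Removal would have to reach about 99.3 to 99.8%. The plan gives no removal figure.

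**Step 4, sensitivity to the particle count.** At 20 pmol, 10⁷ particles gives 1.2 × 10⁶ molecules each, 10⁸ gives 120,000 and 10⁹ gives 12,000. At 100 nm the input would fit by volume from 1.204 × 10¹³ / 81,901 ≈ 1.5 × 10⁸ particles, or 1.204 × 10¹³ / 27,056 ≈ 4.5 × 10⁸ with the larger oligonucleotide volume.

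**Step 5, do the named controls cover it?** Mock-transfected exosomes receive no oligonucleotide, so they have none to carry over. No particle-free arm and no check of the load after clean-up is named in any of the three experiments.

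**The case against.** The strongest reply is that 12 million describes the reaction mix, not what the vesicles hold or the cells receive. Excess reagent in a loading step is not in itself an error. The product is precipitated, spun and resuspended before any cell is treated, and the SOP says its descriptions are brief. All of this stands. A reader might infer that the arms test free-oligonucleotide transfection and not exosomal delivery. The documents do not support that: they do not show how much oligonucleotide survives clean-up. They support only that carry-over is not excluded.

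The size of the excess also rests on one approximate particle count. A reader might think the capacity argument survives even if that count is wrong. It does not at every value: at 10⁹ particles, 12,000 copies each would fit in a 100 nm vesicle. The missing check on carry-over would remain, but this argument for its importance would not.

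A reader might also hold that the dose must match the exercise response, citing the means of 1 and 1.95 in the Aim 3 Design. Those are inputs to the human sample size, not a loading target. The Preliminary Data report a 5-fold rise for stimulated myotubes, and neither figure gives a dose for the inhibitor arms. Matching the dose is a design preference.

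Finally, the plan has other evidence. Unmodified exosomes are applied to adipocytes in Experiments 1.1, 2.2 and 3.2, and GW4869 is used in Experiments 1.4 and 2.1. These bear on whether exosomes act and whether their release matters. They do not show by which route the added mimic or inhibitor acts.

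**Conclusion.** The concern holds as a gap in attribution. At the stated particle count the recipe offers about 150 to 450 times what a 100 nm vesicle could hold (44 to 1,144 times over 73 to 150 nm), and no step or arm shows that the excess is gone before adipocytes are treated. Control-plus, RE-minus, Stim-minus, Pre-plus and Post-minus therefore cannot distinguish vesicle-delivered miR-1 from carried-over oligonucleotide. By themselves they cannot support the necessity and sufficiency claim of Experiments 1.2 and 2.3, or the parallel reading of Experiment 3.2.

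This rests on the 10⁶ particle count, the assumed oligonucleotide volumes, and vesicle sizes measured in mouse serum being applied to human plasma and culture media. The amount of carry-over is unknown. The human miR-1 abundance comparison in Experiment 3.1 and its sample size are unaffected.

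**What to change.** For Experiments 1.2, 2.3 and 3.2, amend the SOP as follows.

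1. Add a particle-free control: oligonucleotide, Exo-fect and ExoQuick-TC without exosomes, taken through the same precipitation and spin and put on adipocytes. Judge the mimic and inhibitor effects against it. In the inhibitor arms, these wells should also receive mock-transfected RE, stimulated or post-exercise exosomes, as appropriate. Otherwise any carried-over inhibitor has no delivered miR-1 to act on, and the control would tell little.
2. After clean-up, measure miR-1 in the mimic-loaded exosomes with the planned qPCR, and report it beside the native post-exercise (or post-stimulation) level. The same assay on the particle-free mimic pellet would give a direct reading of carry-over.
3. Confirm or correct the figure of about 1 × 10⁶ particles.

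Without item 1, limit the conclusion to an effect of miR-1 mimic or inhibitor on adipocytes, with no statement about delivery by exosomes.

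The cost is a few extra wells and qPCR assays, with no added participant procedure or visit. The drawback is that the effect attributable to vesicles may turn out smaller than the uncorrected contrast.

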Catecholamine sensitivity assay. Lipolysis and anti-lipolysis will be measured in 3T3-L1 and ADHAS cells. Cells will be pre-treated for 5 min with adenosine deaminase and then treated with either 10 μ M, 100 μ M, or 1 mM isoproterenol, 0.5 nM insulin, both insulin and 100 μ M isoproterenol, or DMEM only. The cells will be incubated at 37°C for 1 hr with gentle rocking, and the media collected and used for NEFA measurement as previously described by us⁷⁹. To correct for cell surface area, cell diameters will be measured via microscopy^{80,81}.

3T3-L1 adipocyte culture. 3T3-L1 (CL-173, ATCC) adipogenic cells will be maintained in DMEM, 10% FBS and differentiated into adipocytes as previously described by us⁸⁰. Briefly, 3T3-L1 cells will be grown to confluence, then placed in differentiation media (DM), composed of DMEM, 10% FBS, 1 μ M dexamethasone, 0.5 mM isobutylmethylxanthine (IBMX), and 10 μ g/ml insulin for four days. Cells will then be maintained in DM without dexamethasone and IBMX for an additional 3 days⁸². Differentiation to adipocytes will be assessed by Oil Red O staining and expression of the adipocyte-specific mRNA FABP4.

Adult-derived human adipocyte stem cells (ADHASC) culture. Pre-adipocytes were obtained from lipo-aspirate from healthy women undergoing liposuction. Lipo-aspirate was digested using collagenase type I (1 g/l KRB with 1% BSA) for 1 hr at 37°C with gentle shaking. The stromal-vascular fraction was separated from adipocytes by centrifugation, and plated in growth media (DMEM/Hams-F12, 10% fetal bovine serum, and 15 mmol/l HEPES). Following two passages, cells were cryopreserved. Differentiation, as previously described by us^{79,82,83}, will be induced with DM containing 100 nmol/l insulin, 1.0 μ mol/l dexamethasone, 0.25 mmol/l IBMX, 0.033 mmol/l biotin, 0.017 mmol/l pantothenate, and 1.0 μ mol/l rosiglitazone for three days, followed by three additional days using DM without IBMX and rosiglitazone. Differentiation to mature adipocytes will be assessed by Oil Red O staining and FABP4 gene expression.

Specific Aim 1: Determine if exercise-induced exosomal miR-1 enhances adipocyte adrenergic signaling through activation of β 3-AR expression.

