Adipose Biopsy. An abdominal subcutaneous fat biopsy sample will be obtained from the lower abdominal wall prior to and approximately 90 min post exercise. The adipose biopsy procedure is similar to the thigh muscle biopsy procedure, except that 1-2 g of adipose tissue is routinely obtained^{42,79,94,97,98}.

Human serum analyses. Glucose and insulin will be measured in the University of Kentucky CCTS Biochemical Analysis Laboratory^{99,100} from baseline serum collected from fasting lean and obese participants

to calculate HOMA-IR (Glucose*Insulin/405) as a measure of muscle insulin sensitivity. NEFA and free glycerol will be measured ⁸¹ both at baseline and in serum collected at multiple time points following the resistance exercise bout, and used to calculate a simplified “anti-lipolytic index” (NEFA*Insulin), which indicates adipocyte insulin sensitivity based on insulin’s ability to suppress lipolysis ¹⁰¹. In humans, fasting serum norepinephrine is positively associated with isoproterenol ED₅₀ in isolated adipocytes. Thus, elevated fasting catecholamines may be indicative of decreased adipose tissue catecholamine sensitivity ¹⁰². We will also measure serum epinephrine and norepinephrine by HPLC (Vanderbilt University Hormone & Analytical Services Core) ¹⁰³.

Statistical Analysis. The College of Health Sciences supports the effort of a biostatistician through the Office of Research to provide dedicated support to funded investigators. A one-way repeated measures ANCOVA adjusting by sex will be used to determine if a significant difference exists between the groups in response to RE for miR-1 and miR-1A/B primary transcripts. If a significant difference is detected, LSD *post-hoc* comparisons will be performed to identify the source of significance with $p \leq .05$. The Pearson correlation coefficient will be used to determine whether muscle, serum, and adipose miR-1 and miR-1A/B primary transcripts are correlated to tissue insulin sensitivity and fasting catecholamines at baseline. All statistical analyses will be performed using SAS[®] 9.4 (SAS institute, Cary NC).

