We expect that lean individuals will be more insulin sensitive than obese individuals, and that obese participants will display higher fasting NEFA in the context of higher fasting insulin (due to decreased adipose tissue insulin sensitivity). Including both lean and obese individuals will determine if adiposity affects the miR-1 acute response to RE. It is possible that release of miR-1 in exosomes from muscle will be lost or blunted in the obese cohort. However, we hypothesize that insulin sensitivity (assessed by HOMA-IR and the anti-lipolytic index) will be positively correlated to the serum miR-1 excursion following the RE bout in both populations. NEFA and glycerol will be measured both pre- and post-RE to determine whether changes in NEFA and glycerol from baseline are correlated with change in miR-1 in serum and/or adipose from baseline. We will also determine if the induction of adipocyte lipolysis *in vitro* is different in exosomes isolated from lean compared to obese participants following RE. Further, the *in vitro* studies will provide the opportunity to explore additional aspects of adipocyte metabolism that may be regulated by miRs, which will be informed by results of Aims 1 and 2. Overall, we expect results from this study to inform the design of a resistance exercise training trial in obese individuals. Moreover, the proposed studies are expected to provide the fundamental knowledge necessary to determine if exosomal miR-1 delivery to adipose tissue has the potential to form the basis for the development of a novel therapeutic strategy to treat obesity, particularly in individuals physically unable to exercise.

Table 1 provides our projected timeline for the proposed experiments. As discussed above, the preliminary data presented demonstrate that we have the necessary expertise to perform the proposed experiments so we do not anticipate any major delays; however, the experiments have been laid out to accommodate unforeseen delays such that the proposed experiments and analyses will be completed by the end of Year 5.

Table 1. Timetable for proposed experiments.

Specific Aim	Year 1	Year 2	Year 3	Year 4	Year 5
Aim 1: Determine if exercise-induced exosomal miR-1 enhances adipocyte adrenergic signaling through activation of β 3-AR expression.	breed, mature mice to 4 mo., perform Exp 1.1 analyze data	perform Exp 1.3 analyze data	breed, mature mice to 4 mo., perform Exp 1.4 analyze data	write manuscript	

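### The cell assay reads lipolysis and anti-lipolysis from NEFA alone, so the insulin contrast cannot separate less hydrolysis from more re-esterification

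*Combined protocol and SAP*

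**What the plan says.** The Standard Operating Procedures section, under Catecholamine sensitivity assay, sets out what is to be measured: "Lipolysis and anti-lipolysis will be measured in 3T3-L1 and ADHAS cells". There are six arms: three isoproterenol concentrations, DMEM only, and two with insulin, listed as "0.5 nM insulin, both insulin and 100" µM isoproterenol. After one hour the medium is taken, "and the media collected and used for NEFA measurement as previously described" in a cited paper. The only stated adjustment is for cell size: "To correct for cell surface area, cell diameters will be measured via microscopy".

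The gene panel in the same section (including "HSL, ATGL, TGL, PLIN1, FABP2, FABP4") measures mRNA, not fatty-acid flux. No glycerol or re-esterification measure is named for any cell experiment.

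Experiments 1.1, 1.2, 2.2 and 2.3 use this assay for catecholamine sensitivity. Experiment 3.2 uses it for lipolysis in vitro, with exosomes "applied to differentiated ADHASC for 24 hr, and lipolysis" then assessed under the SOP. The titles of Aims 2 and 3 are both worded as claims about adipocyte lipolysis.

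Glycerol does appear in the plan, but only for human serum. Aim 3, Human serum analyses, says "NEFA and free glycerol will be measured" at baseline and after exercise, and the Aim 3 expected outcomes repeat that "NEFA and glycerol will be measured both pre- and post-RE".

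**The concern.** NEFA in the medium is what is left after the cell has recaptured some of the fatty acid it released. One analyte cannot identify two quantities, the amount hydrolysed and the share recaptured. The plan nevertheless attaches the names lipolysis and anti-lipolysis to that one analyte.

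The anti-lipolysis reading is the most exposed. It compares wells with and without insulin. If insulin promotes re-esterification (general physiology, taken here as an assumption because the documents mention only its suppression of lipolysis), part of any fall in NEFA would be counted as suppressed lipolysis when it is not.

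At stake is the wording of the functional conclusion: whether the cell work can support a statement about lipolysis, or only one about net fatty-acid release. The plan pairs NEFA with glycerol in serum but not in the cells where the mechanism is tested.

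**Working it through.** The documents give no figure for this assay, so there is nothing to reproduce. The check is a mass balance with assumed shares.

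**Inputs**
- Analyte: NEFA only (SOP, Catecholamine sensitivity assay).
- Arms: six, of which two contain insulin (same section).
- Re-esterified share *r*: not in the documents; assumed values below.
- Hydrolysis *L*: triglyceride molecules fully hydrolysed, each giving three fatty acids and one glycerol.

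**Formulas**
- NEFA = 3 × *L* × (1 − *r*)
- Glycerol = *L*
- NEFA:glycerol = 3 × (1 − *r*)

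**Step 1: can NEFA tell the two explanations apart?** Start from *L* = 100 and *r* = 0.20.

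| Case | *L* | *r* | NEFA | Glycerol | NEFA:glycerol |
|---|---|---|---|---|---|
| Start | 100 | 0.20 | 3 × 100 × 0.80 = 240 | 100 | 2.4 |
| More re-esterification | 100 | 0.30 | 3 × 100 × 0.70 = 210 | 100 | 2.1 |
| Less lipolysis | 87.5 | 0.20 | 3 × 87.5 × 0.80 = 210 | 87.5 | 2.4 |

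Both changes lower NEFA by 30/240 = 12.5%. NEFA is identical in the two cases; glycerol and the ratio separate them.

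**Step 2: how large could it be?** With *L* fixed, the relative change in NEFA is (1 − *r*₁)/(1 − *r*₀) − 1.
- 10% to 20%: 0.80/0.90 − 1 = −11.1%
- 20% to 30%: 0.70/0.80 − 1 = −12.5%
- 20% to 40%: 0.60/0.80 − 1 = −25.0%
- 30% to 10%: 0.90/0.70 − 1 = +28.6%

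Glycerol changes by 0% in each, by construction of the model.

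**Step 3: which planned contrasts are affected?**

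*Insulin versus no insulin, same exosome condition.* The NEFA ratio is (*L*ins/*L*no) × (1 − *r*ins)/(1 − *r*no). The second factor remains unless insulin leaves *r* unchanged, so this contrast is ambiguous.

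*Exosome condition B versus A, same assay arm.* The NEFA ratio is (*L*B/*L*A) × (1 − *r*B)/(1 − *r*A). If the share is the same in both conditions, the second factor is 1 and the ratio equals *L*B/*L*A. On the difference scale the result is 3 × (1 − *r*) × (*L*B − *L*A), which is scaled but has the right sign. This holds in the insulin arms too, because every exosome condition receives the same insulin. The contrast is disturbed only if the exosome or miR-1 treatment changes *r*.

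**Step 4: do the documents show such a change?** No.
- Preliminary Data groups PLIN1 and FABP2 with the lipolysis genes, and the SOP uses FABP4 as a differentiation marker. None is presented as a marker of re-esterification.
- The Aim 1 alternative approaches report a weaker rise in browning genes in mouse adipose and keep browning as a fallback explanation. That leaves an altered fate of fatty acid open without showing it.
- In 3T3-L1 cells, Preliminary Data reports only non-significant trends in gene expression.

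**The case against.** The strongest reply is that the planned experiments compare exosome conditions, not insulin with no insulin. Insulin is given equally to each condition, as is any insulin carried over from culture, so its effect on re-esterification largely cancels. Four of the six arms contain no added insulin, the assay is named for catecholamine sensitivity, and no experiment states a hypothesis about anti-lipolysis. All of this stands, and it narrows the point considerably.

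It also stands that NEFA release is a legitimate readout. It matches the preliminary adipocyte result and the in vivo index in Aim 3, which multiplies NEFA by insulin. Each experiment also pairs it with gene expression. Demoting NEFA would be a preference, not a correction.

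The shares used above are assumptions, and over a one-hour incubation the effect could be small. If RE exosomes raised re-esterification, the expected rise in NEFA would be understated. A spurious rise would need re-esterification to fall, and the documents give no reason to expect that. The cited assay paper is unavailable and may contain more detail, but the plan's own text names only NEFA.

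These replies do not rescue the anti-lipolysis label. The SOP says anti-lipolysis will be measured, that reading is an insulin versus no-insulin contrast, and nothing cancels there. Nor do they allow a change in NEFA in the isoproterenol arms to be called a change in lipolysis without an unstated assumption about re-esterification.

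**Conclusion.** The point holds in two parts of different strength. For the insulin versus no-insulin comparison, NEFA alone cannot separate suppressed lipolysis from increased re-esterification, so the anti-lipolysis reading is not identified. For exosome contrasts in the isoproterenol-only arms there is an unresolved ambiguity, which matters only if exosome or miR-1 treatment changes the re-esterified share.

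The size is unknown. The assumed shares above give changes in NEFA from −25.0% to +28.6% with no change in lipolysis. They rest on complete hydrolysis, no reuse of glycerol, and shares that the documents do not supply.

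A reader might infer that the functional endpoint of all three aims is biased. The documents do not support that: insulin is common to every exosome condition, and no effect of exosomes on re-esterification is reported. Nor does the point touch the human sample size, which rests on exosomal miR-1, or the Aim 3 statistical analysis, which names miR-1, its primary transcripts and their correlations. This is an inexpensive improvement in what the cell work can claim.

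**What to change.** Measure free glycerol in the same medium aliquots that are already collected for NEFA. Report glycerol, NEFA and the NEFA:glycerol ratio side by side. State in advance that any conclusion about lipolysis or anti-lipolysis rests on glycerol, that NEFA is kept as the fatty-acid release readout comparable with the preliminary data, and that the ratio is the indicator of re-esterification.

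If glycerol is not added, label the endpoint net NEFA release and do not interpret the insulin arms as anti-lipolysis.

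The cost is one extra colorimetric assay per medium sample. A free-glycerol measurement is already planned for serum, and no further participants, biopsies, cultures or incubations are needed. Glycerol has its own limits: it is an imperfect measure where hydrolysis is incomplete or the cell reuses glycerol, and the report should say so.
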